### 15.3 Sample Size and Randomization

The target enrollment for this study is 50 participants, based on a conservative approach to determine the sample size needed to evaluate the effect of ALA supplementation. Two recent studies evaluating the medical management of cystinuric individuals have reported that among individuals who are compliant in taking medications, the average number of stone events per person is approximately 1 per year (Reference #'s 5, 9). The current study design will be powered at 90% to detect a clinically meaningful reduction of stone events at 50% (0.5 stone events per year) with two-tailed  $\alpha = 0.05$ . Based on a two-sided t- test, the following scenarios were considered for the standard deviation (SD) for the sample and sample size (n): SD 0.5, n=11; SD 0.75, n=24; SD 1, n=42. To account for a small dropout rate over the study duration, the enrollment of 50 participants was proposed. At UCSF, clinical volume approximates 60 nephrolithiasis patients per week, including those with cystinuria. At a recent cystinuria outreach event led by [name] at UCSF (<http://[name].ucsf.edu/?q=news/june-18-2015-cystine-patient-symposium>), over 50 individuals with cystinuria attended among over 100 participants overall. We anticipate that 6-8 months will be required to accrue these participants.

Participants will be computer sequence-randomized to receive either ALA or placebo.

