Rationale for Number of Participants	The target enrollment for this study is 50 participants, based on a conservative approach to determine the sample size needed to evaluate the effect of ALA supplementation. Two recent studies evaluating the medical management of cystinuric individuals have reported that among individuals who are compliant in taking medications, the average number of stone events per person is approximately 1 per year (Reference #'s 5, 9). The current study design will be powered at 90% to detect a clinically meaningful reduction of stone events at 50% (0.5 stone events per year) with two-tailed $\alpha = 0.05$ . Based on a two-sided t-test, the following scenarios were considered for the standard deviation (SD) for the sample and sample size (n): SD 0.5, n=11; SD 0.75, n=24; SD 1, n=42. To account for a small dropout rate over the study duration, the enrollment goal of 50 participants was proposed.

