Clinical data including medical history, plain KUB x-ray and renal ultrasound, routine blood work, and 24-hour urine collections for all participants will be collected as part of normal clinical care at routine clinical visit intervals, which currently occur every 4 months. Routine clinical care for participants will not be altered in any way outside of administration of the supplement or placebo. Routine clinical care generally consists of office visits every 4 months at which time, as medically necessary as determined by the study investigator, an imaging study is performed (plain KUB x-ray, ultrasound, or CT scan if clinically indicated), a 24-hour urine collection is done to check quantitative urinary cystine levels, and blood is drawn to evaluate electrolyte levels as well as renal function. During routine visits for blood and urine tests, any discarded blood and urine specimens will be collected for research testing. No additional blood draw or urine collection will be performed for this study. From discarded routine specimens provided during these clinic visits, metallomic and metabolomics profiling will be performed for all participants using discarded samples material. This is comprised of mass spectrometry and elemental analysis of samples performed in our research lab. Quality of life measurement, as recorded by the Wisconsin Stone-quality of life questionnaire (Wisconsin Stone-QoL), will also be evaluated.

Recurrent stone events, defined by symptomatic or silent stone recurrence, is the primary endpoint in this study. It will be documented in this study cohort, and compared between treatment and placebo groups to determine treatment effect. If stones are removed for surgery or spontaneously passed by participants, any discarded stone specimens not needed for clinical care will also be subjected to metabolomic and metallomic analysis.

At the end of the three years of study drug treatment, all participants will undergo a low dose non-contrast CT scan to look for a silent change in stone size. As this is a pilot study, recruitment will be limited to target enrollment of 50 participants (25 for each treatment arm). Treatment will continue for a total of 3 years and after treatment completion, participants will be followed for an additional 2 years to evaluate for change in clinical status or adverse events resultant from ALA administration.

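### The sample sizes 11, 24 and 42 fit a one-sample formula; with 25 per arm the claimed 90% power holds only if the SD is about 0.53 or less

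*Combined protocol and SAP*

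**What the plan says.** The sample-size rationale appears in section 15.3 and, almost word for word, in the synopsis (Rationale for Number of Participants).

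- **Control rate:** in compliant patients "the average number of stone events per person is approximately 1 per year".
- **Target effect:** a "reduction of stone events at 50% (0.5 stone events per year"), with 90% power and two-tailed alpha 0.05.
- **Method:** "Based on a two-sided t- test, the following scenarios were considered" for the SD and n.
- **Result:** "SD 0.5, n=11; SD 0.75, n=24; SD 1, n=42". The text does not say whether n is per arm or total.
- **Enrolment:** "To account for a small dropout rate over the study duration, the enrollment of 50 participants was proposed". No dropout rate is given.

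Section 4.1 calls the study a pilot and fixes the allocation: "recruitment will be limited to target enrollment of 50 participants (25 for each treatment arm"). The synopsis (Primary Analysis Plan) says that stone recurrence rates in the ALA and placebo groups will be compared by a two-sided t-test. Section 15.2 adds only that the analysis follows intention to treat.

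**The concern.** A two-arm comparison has sampling error from both arms. For the same difference, SD, alpha and power it needs about twice the one-sample number in each arm, so about four times that number in total. The listed values are too small for two arms, and the step from 42 to 50 suggests that 42 was taken as the whole trial at SD 1.

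The 90% claim carries no condition, and the rationale is described as conservative. If the true power is far lower, a null result would be read as good evidence against a 50% reduction when the trial had little chance of showing one. Anyone judging whether the trial can answer its primary question would also be relying on a wrong figure.

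**Working it through.** **Inputs.** Difference 0.5 events per year, two-sided alpha 0.05, power 90%, and SD 0.5, 0.75 or 1 (section 15.3 and synopsis). Two parallel arms of 25 (section 4.1). Between-arm t-test (synopsis). SD is taken as the between-person SD of the annualised event rate, because the plan sets it directly against a difference in events per year.

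**1. Reproducing the plan's n.** The one-sample normal formula is n = (1.960 + 1.2816)² × SD² / 0.5².

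| SD | One-sample n | Plan's n |
|---|---|---|
| 0.5 | 10.51 | 11 |
| 0.75 | 23.64 | 24 |
| 1 | 42.03 | 42 |

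All three match to the nearest whole number. Two-sample calculations do not give this set. By the normal formula, per arm:

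- two-sided, 90% power: 22, 48, 85
- one-sided, 90% power: 18, 39, 69
- two-sided, 80% power: 16, 36, 63
- one-sided, 80% power: 13, 28, 50

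**2. The two-arm requirement.** The normal formula is n per arm = 2 × (1.960 + 1.2816)² × SD² / 0.5² = 21.0, 47.3, 84.1. The exact (noncentral t) calculation gives slightly more:

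| SD | Per arm for 90% | Total | Power, 25 per arm | Power, 21 per arm |
|---|---|---|---|---|
| 0.5 | 23 | 46 | 93% | 89% |
| 0.75 | 49 | 98 | 64% | 56% |
| 1 | 86 | 172 | 41% | 35% |

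The 21-per-arm column is illustrative. It takes the loss implied by going from 42 to 50, which is (50 − 42)/50 = 16%.

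**3. Both readings of 42 at SD 1.**

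- As a total, it means 21 per arm and 35% power.
- As a per-arm number, it gives 62% power and needs 84 participants, which contradicts the enrolment of 50.

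**4. What 25 per arm can support.** The largest SD that keeps 90% power is 0.53 with all 50 evaluable, or 0.49 with 21 per arm. The difference detectable with 90% power is 0.47, 0.70 and 0.94 events per year at the three SDs. The expected 95% confidence-interval half-width is t(0.975, 48 df) × SD × √(2/25) = 2.011 × 0.2828 × SD, which is 0.28, 0.43 and 0.57 events per year.

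**5. Is an SD of 0.5 plausible?** The plan gives no source for any SD. As an illustration, suppose pure Poisson counts at 1 and 0.5 per year over 3 years, with no differences between patients. The rate variances are 1/3 and 0.5/3, so the pooled SD is √((1/3 + 0.5/3)/2) = 0.50. Differences between patients raise it. If true rates vary between patients with a gamma variance of 0.25 × mean², the SD is √((0.333 + 0.25 + 0.167 + 0.0625)/2) = 0.64 and power at 25 per arm is 78%. With 0.5 × mean², the SD is 0.75 and power is 64%. These two variances are assumptions, not figures from the plan.

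**The case against.** Four objections deserve an answer.

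- **The formula is inferred.** The plan names only a two-sided t-test, and an exact one-sample t calculation would give 13, 26 and 44. This stands as a caution about where the figures came from. The conclusion does not depend on it, since 11, 24 and 42 are not two-arm sizes for 90% power whatever produced them.
- **The SD might be that of a one-year count.** Averaging three independent years, which is optimistic, would turn 0.5, 0.75 and 1 into 0.29, 0.43 and 0.58. Power at 25 per arm would then be above 99%, 98% and 85%. The plan does not state this reading, and it does not produce 11, 24 and 42. Even here, SD 1 falls short of 90% (78% with 21 per arm). It does show that the SD must be defined.
- **The SD may really be near 0.5.** Then power with all 50 evaluable is 93%. The documents cannot exclude this. But 0.5 is the most favourable of the plan's three scenarios and equals the Poisson value with no differences between patients, whereas 50 was derived from SD 1.
- **It is a declared pilot, and losses may be small.** Section 12.1 encourages participants who stop treatment to complete the remaining visits, so 16% is illustrative only. The pilot label justifies a small trial, but it does not make the 90% statement correct.

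**Conclusion.** The concern holds. The stated sizes are about a quarter of the total that a two-arm comparison needs. With 25 per arm the trial has 93%, 64% and 41% power at the plan's three SDs, and the 90% claim is true only for an SD up to about 0.53 with no missing outcomes.

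The two-arm requirement follows from the plan's own difference, alpha, power and SDs. The power figures also assume that SD means the between-person SD of the annualised rate, that it is equal in both arms, and that the t-test is adequate for event rates. The documents do not show which SD applies, so true power is uncertain. The unconditional 90% statement is wrong as written and must be corrected.

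**What to change.** In section 15.3 and the synopsis:

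1. Replace 11, 24 and 42 with 23, 49 and 86, labelled per arm (46, 98 and 172 in total, before dropout).
2. Remove the unconditional 90% claim and the description of the approach as conservative. State that 25 per arm gives 93%, 64% and 41% power at SD 0.5, 0.75 and 1.
3. Define the SD (per-person annualised rate over 3 years, or otherwise) and give its source.
4. State the assumed dropout rate and the power after it. At an illustrative 16%, power is 89%, 56% and 35%.
5. Present the trial as the pilot that section 4.1 describes, with the expected 95% confidence-interval half-width (0.28, 0.43 and 0.57 events per year) as its planned precision.

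The cost is a change of wording in two places and a less favourable stated power. The correction needs no change to visits, treatment or enrolment. If the sponsor wants to keep 90% power at an SD above about 0.53, the sample size would have to rise accordingly.

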## 16 DATA COLLECTION, RETENTION AND MONITORING

### 16.1 Data Collection Instruments

The Investigator will prepare and maintain adequate and accurate source documents designed to record all observations and other pertinent data for each participant treated with the study drug.

Entry will be performed electronically by the study coordinator directly into UCSF REDCap, a HIPAA-compliant data management system incorporated into the UCSF electronic medical record system, or uploaded in an automated fashion from our electronic medical record into REDCap. Participants will not be identified by name in the study database or on any study documents to be collected by the Sponsor (or designee), but will be identified by a participant number.

If a correction is required for any data entry, the time and date stamps track the person entering or updating data and creates an electronic audit trail.

The Investigator is responsible for all information collected on participants enrolled in this study. All data collected during the course of this study must be reviewed and verified for completeness and accuracy by the Investigator. A copy of the CRF will remain at the Investigator's site at the completion of the study.

### 16.2 Data Management Procedures

The data will be entered into a REDCap database. All procedures for the handling and analysis of data will be conducted using good computing practices meeting FDA guidelines for the handling and analysis of data for clinical trials.

### **16.3 Data Quality Control and Reporting**

After data have been entered into the study database, a system of computerized data validation checks will be implemented and applied to the database on a regular basis. Queries are entered, tracked, and resolved through the REDCap system directly. The study database will be updated in accordance with the resolved queries. All changes to the study database will be documented.

### **16.4 Archival of Data**

The database is safeguarded against unauthorized access by established security procedures; appropriate backup copies of the database and related software files will be maintained.

All electronic files containing personal identifiers will be stored only on the UCSF site file servers located behind a firewall. Information transferred to the server for backup purposes will be done via secure ftp. Files may be transferred to other computers temporarily via the Internet to facilitate central upload. In these circumstances, the files will be protected by encryption. The UCSF site file servers are only accessible by network support specialists in locked rooms. The on-site file server will be electronically accessible only to study investigators through user password protection. No non-electronic files (such as paper surveys, consent forms, pathology data, etc.) will be kept for this study. Databases are backed up by the database administrator in conjunction with any updates or changes to the database.

At critical junctures of the protocol (e.g., production of interim reports and final reports), data for analysis is locked and cleaned per established procedures.

### **16.5 Availability and Retention of Investigational Records**

The Investigator must make study data accessible to the authorized representatives of the Sponsor (or designee), IRB/IEC, and Regulatory Agency (e.g., FDA) inspectors upon request. A file for each participant must be maintained that includes the signed Informed Consent, HIPAA Authorization and Assent Form and copies of all source documentation related to that participant. The Investigator must ensure the reliability and availability of source documents from which the information on the CRF was derived.

All study documents (participant files, signed informed consent forms, copies of CRFs, Study File Notebook, etc.) must be kept secured for a period of two years following marketing of the investigational product or for two years after centers have been notified that the IND has been discontinued. There may be other circumstances for which the Sponsor is required to maintain study records and, therefore, the Sponsor should be contacted prior to removing study records for any reason.

### **16.6 Monitoring**

Monitoring will be conducted by the Sponsor according to the U.S. CFR Title 21 Parts 50, 56, and 312 and ICH Guidelines for GCP (E6). By signing this protocol, the Investigator / Sponsor (or designee), will allow appropriate regulatory authorities to conduct on-site monitoring and/or auditing of all appropriate study documentation.

## **16.7 Participant Confidentiality**

Clinical data for these participants will be collected in our REDCap database, which is a secure, online HIPAA-compliant research data collection portal.

## **17 ADMINISTRATIVE, ETHICAL, REGULATORY CONSIDERATIONS**

The study will be conducted according to the Declaration of Helsinki, Protection of Human Volunteers (21 CFR 50), Institutional Review Boards (21 CFR 56), and Obligations of Clinical Investigators (21 CFR 312).

To maintain confidentiality, all laboratory specimens, evaluation forms, reports and other records will be identified by a coded number only. All study records will be kept in a locked file cabinet and code sheets linking a participant's name to a participant identification number will be stored separately in another locked file cabinet. Clinical information will not be released without written permission of the participant, except as necessary for monitoring by the FDA. The Investigator must also comply with all applicable privacy regulations (e.g., Health Insurance Portability and Accountability Act of 1996, EU Data Protection Directive 95/46/EC).

### **17.1 Protocol Amendments**

Any amendment to the protocol will be written by the Sponsor/Investigator. Protocol amendments cannot be implemented without prior written IRB/IEC approval except as necessary to eliminate immediate safety hazards to participants. A protocol amendment intended to eliminate an apparent immediate hazard to participants may be implemented immediately, provided the IRBs are notified within five working days.

### **17.2 Institutional Review Boards and Independent Ethics Committees**

The protocol and consent form will be reviewed and approved by the IRB/IEC prior to study initiation. Serious adverse experiences regardless of causality will be reported to the IRB/IEC in accordance with the standard operating procedures and policies of the IRB/IEC, and the Investigator will keep the IRB/IEC informed as to the progress of the study. The Investigator will obtain assurance of IRB/IEC compliance with regulations.

Any documents that the IRB/IEC may need to fulfill its responsibilities (such as protocol, protocol amendments, Investigator's Brochure, consent forms, information concerning participant recruitment, payment or compensation procedures, or other pertinent information) will be submitted to the IRB/IEC. The IRB/IECs written unconditional approval of the study protocol and the informed consent form will be in the possession of the Investigator before the study is initiated. The IRB/IECs unconditional approval statement will be transmitted by the Investigator to the FDA prior to the shipment of study supplies to the site. This approval must refer to the study by exact protocol title and number and should identify the documents reviewed and the date of review.

Protocol and/or informed consent modifications or changes may not be initiated without prior written IRB/IEC approval except when necessary to eliminate immediate hazards to the participants or when the change(s) involves only logistical or administrative aspects of the study. Such modifications will be submitted to the IRB/IEC and written verification that the modification was submitted and subsequently approved should be obtained.

The IRB/IEC must be informed of revisions to other documents originally submitted for review; serious and/or unexpected adverse experiences occurring during the study in accordance with the standard operating procedures and policies of the IRB; new information that may affect adversely the safety of the participants of the conduct of the study; an annual update and/or request for re-approval; and when the study has been completed.

### **17.3 Informed Consent Form**

Informed consent will be obtained in accordance with the Declaration of Helsinki, ICH GCP, US Code of Federal Regulations for Protection of Human Subjects (21 CFR 50.25[a,b], CFR 50.27, and CFR Part 56, Subpart A), the Health Insurance Portability and Accountability Act (HIPAA, if applicable), and local regulations.

The Investigator will prepare the informed consent form, assent and HIPAA authorization and provide the documents to the Sponsor or designee for approval prior to submission to the IRB/IEC. The consent form generated by the Investigator must be acceptable to the Sponsor and be approved by the IRB/IEC. The written consent document will embody the elements of informed consent as described in the International Conference on Harmonisation and will also comply with local regulations. The Investigator will send an IRB/IEC-approved copy of the Informed Consent Form to the Sponsor (or designee) for the study file.

A properly executed, written, informed consent will be obtained from each participant prior to entering the participant into the trial. Information should be given in both oral and written form and s participants (or their legal representatives) must be given ample opportunity to inquire about details of the study. If appropriate and required by the local IRB/IEC, assent from the participant will also be obtained. If a participant is unable to sign the informed consent form (ICF) and the HIPAA authorization, a legal representative may sign for the participant. A copy of the signed consent form (and assent) will be given to the participant or legal representative of the participant and the original will be maintained with the participant's records.

### **17.4 Publications**

The preparation and submittal for publication of manuscripts containing the study results shall be in accordance with a process determined by mutual written agreement among the study Sponsor/Investigator. The publication or presentation of any study results shall comply with all applicable privacy laws, including, but not limited to, the Health Insurance Portability and Accountability Act of 1996.

### **17.5 Investigator Responsibilities**

By signing the Agreement of Investigator form, the Investigator agrees to:

1. Conduct the study in accordance with the protocol and only make changes after notifying the Sponsor (or designee), except when to protect the safety, rights or welfare of participants.
2. Personally conduct or supervise the study (or investigation).

3. Ensure that the requirements relating to obtaining informed consent and IRB review and approval meet federal guidelines, as stated in § 21 CFR, parts 50 and 56.
4. Report to the Sponsor or designee any AEs that occur in the course of the study, in accordance with §21 CFR 312.64.
5. Ensure that all associates, colleagues and employees assisting in the conduct of the study are informed about their obligations in meeting the above commitments.
6. Maintain adequate and accurate records in accordance with §21 CFR 312.62 and to make those records available for inspection with the Sponsor (or designee).
7. Ensure that an IRB that complies with the requirements of §21 CFR part 56 will be responsible for initial and continuing review and approval of the clinical study.
8. Promptly report to the IRB and the Sponsor (or designee) all changes in the research activity and all unanticipated problems involving risks to participants or others (to include amendments and IND safety reports).
9. Seek IRB approval before any changes are made in the research study, except when necessary to eliminate hazards to the participants.
10. Comply with all other requirements regarding the obligations of clinical investigators and all other pertinent requirements listed in § 21 CFR part 312.

